APPENDIX 3: Trial management

Trial Management

1.8. Trial Management and Oversight

Trial Management Group (TMG)

The TMG, led by the CI ([name]) will comprise all Investigators, the Trial Manager, Research and Administrative staff, with input from patient / public representatives. The TMG will be responsible for trial design, conduct, management, strategy, costs, data analyses and publication. With the support of all Centre staff, the Trial Manager, will be responsible for operationalising TMG strategy and day to day trial management. The TMG will meet monthly to review detailed monitoring information regarding trial progress against the

APPENDIX 3: Trial management

milestones outlined in the Gantt chart. Most meetings will be by teleconference, but the TMG will also meet face to face biannually.

Centre Management Groups

Located in Bristol, Cardiff and Southampton, trial centre management groups will take responsibility for Centre recruitment, with Centre PIs ([name], [name] and [name]) meeting with Centre teams weekly/fortnightly as required. The Trial Manager will lead monthly Team Meeting teleconferences (taking place between the monthly TMGs), consisting of all Centre staff (trial coordinators, nurses and administrators) to operationalise TMG strategy.

Trial Steering Committee (TSC)

The Trial Steering Committee (TSC) will meet twice a year to provide independent supervision of the trial on behalf of the NIHR HTA. Members of the TSC are independent, i.e. have no direct involvement in the trial. In particular, the TSC will focus on trial recruitment, adherence to the protocol, patient safety and consideration of new information. We will ask an experienced, independent academic GP to chair the TSC, and independent members will include another clinical triallist, a statistician and PPI representation. Representation will be invited from the Sponsor and the NIHR HTA. The TSC will have the flexibility to meet annually or biannually depending on trial progress.

The membership will include:

- [name], University of Cambridge (Chair)
- [name], Professor of Child Health & Head of Division of Child Health, Obstetrics & Gynaecology (COG), University of Nottingham
- [name], GP and Academic Clinical Lecturer, Nuffield Department of Primary Care Health Sciences, University of Oxford
- CEDAR Trial CI ([name])
- One or two investigators, in line with HTA guidance
- PPI representation

Trial co-ordinators, statisticians etc will also be invited to attend as appropriate.

The TSC terms of reference can be found in Appendix 5.

Data Monitoring Committee

The Data Monitoring Committee (DMC) will meet twice a year, shortly before each TSC, to advise and make recommendations to the TSC regarding trial safety issues, or other reasons for the trial not to continue. If necessary, the DMC will have access to unblinded trial data. Members of the DMC are independent, i.e. have no direct involvement in the trial. The membership will include:

- [name], Professor of Medical Statistics, Dept of Primary Care and Public Health Sciences, King's College London (Chair)
- [name], Professor of General Practice Research, Primary Care Sciences, Keele University, [name]
- [name], Trial Statistician, Dept of Primary Care and Public Health Science, King's College London
- CEDAR Trial CI ([name])
- CEDAR Trial Statistician ([name])

The DMC terms of reference can be found in Appendix 6.

Trial Sponsor

The trial sponsor will be the University of Bristol, and will ensure the trial meets its contractual, legal, insurance, and financial obligations, and is conducted in line with UK Clinical Trial Regulations.
APPENDIX 3: Trial management

Data quality

Data quality will be monitored and assured throughout recruitment by: (i) the Responsible Clinician accurately entering data to the web-based data collection system (e-CRF); (ii) a random 20% sample paper symptom diaries being checked against web-based data entry by the research team; (iii) recruiting sites conducting a self-audit after recruiting their first four patients; and (iv) a random 10% sample of e-CRFs will be checked by the research team. Sponsor monitoring will be undertaken in line with a risk based monitoring plan.

APPENDIX 4: Investigative Team Expertise

[name] is an experienced multi-centre study manager who, as part of a multidisciplinary team, has overseen the successful recruitment and retention of over 5,000 children to the NIHR HTA funded DUTY study, and the successful recruitment of participants to the NIHR NSPCR funded OSAC trial.

We believe there are six key factors that will ensure the success of the CEDAR trial:

- 1. We have excellent links with the NIHR Primary Care Research Networks and strong personal relationships with regional primary care sites, who have recruited over 15,000 children to our NIHR-funded studies of acute infection in the past 5 years alone.
- 2. Our PPI group reports that parents are interested to try the drops, which will only be available through the trial (they are not available over-the-counter (OTC) or through the NHS), and as describe above, many parents will be aware of the trial via GP practice notification letters.
- 3. Given the current therapeutic limitations for ear pain in children (paracetamol and/or ibuprofen), we believe clinicians will be interested in and want to support the trial.
- 4. The 'light-touch' recruitment process that will fit with usual care processes and minimise disruption.
- 5. High rates of primary outcome ascertainment with outcomes available by the end of the first week of participation, facilitated by using tried and tested, light-touch combined paper, online and telephone data collection systems. Similar systems used in our previous studies have achieved primary outcome follow up rates in excess of 90%⁶⁷.
- 6. The use of qualitative methods to assess parent attitudes to trial participation, which will provide early warning of unanticipated challenges to the Trial Management Group (TMG).

APPENDIX 5: Trial Steering Committee Terms of Reference

The role of the TSC/SSC

The role of the TSC/SSC is to provide overall supervision for a trial on behalf of the Trial Sponsor and Trial Funder and to ensure that the trial is conducted to the rigorous standards set out in the Department of Health's Research Governance Framework for Health and Social Care and the Guidelines for Good Clinical Practice. It should be noted that the day-to-day management of the trial is the responsibility of the Chief Investigator, and as such the Chief Investigator may wish to set up a separate Trial Management Group (TMG) to assist with this function.

The main features of the TSC/SSC are as follows:

- To provide advice, through its Chair, to the Chief Investigator(s), the Trial Sponsor, the Trial Funder, the Host Institution and the Contractor on all appropriate aspects of the trial
- To concentrate on progress of the trial, adherence to the protocol, patient safety and the consideration of new information of relevance to the research question
- The rights, safety and well-being of the trial participants are the most important considerations and should prevail over the interests of science and society
- To ensure appropriate ethical and other approvals are obtained in line with the project plan
- To agree proposals for substantial protocol amendments and provide advice to the sponsor and funder regarding approvals of such amendments
- To provide advice to the investigators on all aspects of the trial

Standard Constitution TSC/SSC

The following list identifies the minimum constitution requirements, a set of outline terms of reference, and the primary reporting line for TSCs/SSCs:

- All primary research projects are required to establish a TSC (or occasionally a SSC)
- The NIHR HTA Programme Director will vet the nominees and appoint the chair and members
- All TSCs/SSCs are to have an independent chair
- All TSCs/SSCs are to have a minimum of 75% majority of independent members
- Only appointed members will be entitled to vote and the chair will have a casting vote
- The minimum quoracy for a meeting to conduct business is 67% of appointed members
- The chair and members to sign and maintain a log of potential conflicts and/or interests
- Attendance at TSC/SSC meetings by non-members is at the discretion of the chair
- The primary TSC/SSC reporting line is via the chair to the NIHR HTA Programme Director

Composition of the TSC/SSC

- The HTA Programme does not accept generic CTU TSCs
- An independent chair (UK based and/or holding a substantive UK based appointment)
- Independent clinicians with relevant expertise
- Independent statisticians/epidemiologists/diagnosticians with relevant expertise
- At least one individual who is able to contribute a patient and/or wider public perspective.
- Ideally, the TSC/SSC should invite observers, including a representative of the sponsor and a representative from the research network to meetings
- An indication of any proposed overseas members should have been given at the full application stage and feedback on such proposals supplied following the Commissioning Board's consideration of the application
- Although there may be periods when more frequent meetings are necessary, the TSC/SSC should meet at least annually
- Meetings should be scheduled to follow shortly after DM(E)C meetings so that reports from that group can be considered
- Minutes of meetings should be sent to all members, the sponsor, the funder and the trial master file

APPENDIX 5: Trial Steering Committee Terms of Reference

The responsibility for calling and organising TSC/SSC meetings lies with the Chief Investigator, in association with the Chair.

There may be occasions when the Trial Sponsor or the Trial Funder will wish to organise and administer these meetings for particular trials. In the NIHR HTA programme's case this is unlikely, but it reserves the right to attend any meeting and the right to convene a meeting of the TSC/SSC in exceptional circumstances.

The Role of the Chair of TSC/SSC

The Chair of the TSC/SSC is directly answerable to the NIHR HTA programme, as funder. The Chair's responsibilities include:

- Arranging an inaugural meeting to finalise the protocol and to set up a schedule of meetings to align with the project plan
- Establishing clear reporting lines to the Funder, Sponsor, etc.
- Being familiar with relevant guidance documents and with the role of the DM(E)C
- Providing an independent, experienced opinion if conflicts arise between the needs of the research team, the funder, the sponsor, the participating organisations and/or any other agencies
- Leading the TSC/SSC to provide regular, impartial oversight of the trial, especially to identify and pre-empt problems
- Ensuring that changes to the protocol are debated and endorsed by the TSC/SSC; letters of endorsement should be made available to the project team when requesting approval from the funder and sponsor for matters such as changes to protocol
- Being available to provide independent advice as required, not just when TSC/SSC meetings are scheduled
- Commenting on any extension requests and, where appropriate, providing a letter of recommendation to accompany such a request
- Commenting in detail (when appropriate) regarding the continuation or termination of the project

Independence

The definition of independent is as follows:

- Not part of the same institution as any of the applicants or members of the project team
- Not part of the same institution that is acting as a recruitment or investigative centre
- Not related to any of the applicants or members of the project team
- For the chair only not an applicant on a rival proposal.

APPENDIX 6: Data Monitoring Committee Terms of Reference

The role of the DM(E)C

The DMECs main role is as follows:

- It is the only body involved in a trial that has access to the unblinded comparative data
- The role of its members is to monitor these data and make recommendations to the TSC/SSC on whether there are any ethical or safety reasons why the trial should not continue
- The safety, rights and well-being of the trial participants are paramount
- The DM(E)C considers the need for any interim analysis advising the TSC/SSC regarding the release of data and/or information
- The DM(E)C may be asked by the TSC/SSC, Trial Sponsor or Trial Funder to consider data emerging from other related studies
- If funding is required above the level originally requested, the DM(E)C may be asked by the Chief Investigator, TSC/SSC, Trial Sponsor or Trial Funder to provide advice and, where appropriate, information on the data gathered to date in a way that will not compromise the trial
- Membership of the DM(E)C should be completely independent, small (3- 4 members) and comprise experts in the field, e.g. a clinician with experience in the relevant area and expert trial statistician
- Responsibility for calling and organising DM(E)C meetings lies with the Chief Investigator, in association
 with the Chair of the DM(E)C. The project team should provide the DM(E)C with a comprehensive report,
 the content of which should be agreed in advance by the Chair of the DM(E)C
- The DM(E)C should meet at least annually, or more often as appropriate, and meetings should be timed so that reports can be fed into the TSC/SSC
- Minutes of meeting should be sent to all members, the sponsor, the funder, the TSC and the trial master file. It should be noted that the minutes may have 'in camera' items redacted from some copies

Standard Constitution DM(E)C

The following list identifies the minimum constitution requirements, a set of outline terms of reference and the primary reporting line for DM(E)C:

- Most primary research projects are required to establish a DM(E)C
- The NIHR HTA Programme Director will vet the nominees and appoint the chair and members
- All DM(E)C members are to be independent (with at least one member being UK based and/or holding a substantive UK based appointment)
- Only appointed members will be entitled to vote and the chair will have a casting vote
- The minimum quoracy for a meeting to conduct business is 67% of appointed members
- The chair and members to sign and maintain a log of potential conflicts and/or interests
- Attendance at DM(E)C meetings by non-members is at the discretion of the chair
- The primary DM(E)C reporting line is via the chair to the TSC/SSC

Independence

The definition of independent is as follows:

- Not part of the same institution as any of the applicants or members of the project team
- Not part of the same institution that is acting as a recruitment or investigative centre
- Not related to any of the applicants or members of the project team
- For the chair only- not an applicant on a rival proposal

APPENDIX 7: Study outcome definition and measurement

Research question	Question and outcome type	Outcome measure	Presented as	Method of outcome data collection
1.1 Do active drops lead to a lower proportion of children consuming antibiotics by Day 8 (where Day 1 is the day of randomisation) compared with no drops (usual care)?	Primary	Binary (yes/no): 'any antibiotics' consumed by Day 8 vs 'none'	The proportion of children recruited who have been given any antibiotics by mouth within the first 7 days post randomisation	Daily Symptom and Recovery Questionnaire (Days 1-8) with telephone support calls during week 1; GP records
2.1 Do active drops provide superior pain relief in the first 24-36 hours compared to placebo drops?	Key secondary	Ordinal: Parent-rated child's ear pain score at 24-36 hours, using the zero to ten rating scale	Mean/Median/Log mean ear pain score (0-10) over the 24- 36 hours since randomisation (depending on the distribution).	Daily Symptom and Recovery Questionnaire (Days 1-8) with telephone support calls during week 1
2.2 Do active drops lead to reduced oral analgesic consumption in the first 7 days after randomisation compared with placebo drops?	Secondary	Numeric: Analgesic use at Day 8 = number of doses of paracetamol and/or ibuprofen and/or other pain- relieving agents	Mean/Median/Log mean number of doses in the first 7 days after randomisation (depending on the distribution).	Daily Symptom and Recovery Questionnaire (Days 1-8) with telephone support calls during week 1
2.3 Do placebo drops provide superior pain relief in the first 24-36 hours compared to 'no drops' (usual care)?	Secondary	Ordinal: Parent-rated child's ear pain score at 24-36 hours, using the zero to ten rating scale	Mean/Median/Log mean ear pain score (0-10) over the 24- 36 hours since randomisation (depending on the distribution).	Daily Symptom and Recovery Questionnaire (Days 1-8) with telephone support calls during week 1
2.4 Do active drops lead to a lower proportion of children consuming antibiotics by Day 8 (where Day 1 is the day of randomisation) compared with placebo drops?	Secondary	Binary: 'any antibiotics' consumed by Day 8 vs 'none'	The proportion of children recruited who have taken any antibiotics by mouth within the first 7 days post randomisation	Daily Symptom and Recovery Questionnaire (Days 1-8) with telephone support calls during week 1
2.5 Do active drops alter the number of days before starting antibiotics in the first seven days post randomisation, compared with placebo drops and no drops (usual care)?	Secondary	Numeric: number of days post randomisation to first consuming antibiotics	For children who have started taking antibiotics, the average number of days after recruitment for which antibiotics were not given (delayed)	Daily Symptom and Recovery Questionnaire (Days 1-8) with telephone support calls during week 1

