5.3. Primary Research Question

The *main aim* of the CEDAR trial is to investigate the clinical and cost effectiveness of benzocaine/ phenazone (hereon 'active') ear drops compared to 'no drops' (usual care) for reducing antibiotic consumption and ear pain in children aged between 12 months and 10 years presenting to primary care with AOM.

Main research question:

5.3.1. **[Primary research question]** Do active drops lead to a lower proportion of children consuming antibiotics by Day 8 (where Day 1 is the day of randomisation) compared with no drops (usual care)?

5.4. Secondary Research Questions:

- 5.4.1. **[Key secondary research question]** Do active drops provide superior pain relief in the first 24-36 hours compared to placebo drops?
- 5.4.2. Do active drops lead to reduced oral analgesic consumption in the first 7 days after randomisation compared with placebo drops?
- 5.4.3. Do placebo drops provide superior pain relief in the first 24-36 hours after randomisation compared to 'no drops' (usual care)?
- 5.4.4. Do active drops provide superior pain relief during Day 1 (day of consultation) compared to placebo drops? (Measured at approximately 1 hour after administration of the drops and on the evening of Day 1)
- 5.4.5. Do active drops lead to a lower proportion of children consuming antibiotics by Day 8 compared with placebo drops?
- 5.4.6. Do active drops alter the number of days before starting antibiotics in the first seven days post randomisation, compared with placebo drops and no drops (usual care)?
- 5.4.7. Do active drops reduce overall symptom burden (including episodes of crying/ distress, disturbed sleep, interference with normal activity, appetite and fever) in the first 7 days after randomisation compared to placebo drops and no drops (usual care)?
- 5.4.8. Do active drops alter overall illness duration (defined as the last day post randomisation on which parent-reported child ear pain scores zero for two consecutive days without other analgesic medication) compared to placebo drops and no drops (usual care)?
- 5.4.9. What are the net incremental costs to the NHS (e.g. fewer antibiotic prescriptions) and society (e.g. parental productivity) of using active ear drops compared to no drops (usual care) in the short (7 days post randomisation) and medium term (3 months)?

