12. ANALYSIS

12.1. Sample size calculation

Antibiotic consumption (primary outcome)

Current United Kingdom (UK) antibiotic prescribing rates are high for children with AOM, in fact higher than for any other respiratory infection of childhood.⁸ One study showed prescribing rates of 84%,⁹ while another showed three-quarters of UK general practices prescribe antibiotics to at least 80% of children with AOM.⁸ We are not aware of any evidence to inform consumption rate, but our clinical experience and PPI group suggest that the majority of parents will give their child a prescribed antibiotic. Our power calculation therefore (conservatively) assumes a no drop (usual care) arm antibiotic consumption rate of 80 to 90%. While it is agreed that for reducing the development of antimicrobial resistance, antibiotic consumption is more meaningful than prescribing, there is no agreed minimum difference in antibiotic consumption worth detecting. Our work has shown a clear and prolonged link between primary care prescribed antibiotics and antimicrobial resistance lasting over 6 months,¹⁰ and although we did not find evidence to define a clinically important difference in consumption rates, these data¹⁰ suggest that a 20% change in consumption could have important effects on antimicrobial resistance, both in children and in their infectious contacts. Assuming a Type II error rate of 0.1 (90% power) and Type I error rate of 0.05 (alpha) the number of children needed in each group (active eardrops and no drops) ranges from 92 to 119 to demonstrate a 20% fall in antibiotic consumption from 80-90% in the control group to 60-70%. Using the more conservative estimate of 119, and taking into account 20% attrition, this would give a final sample size of 149 per arm.

Pain (secondary outcome)

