12.5. Statistical analysis

Quantitative analysis

The analysis and presentation of the trial will be in accordance with the CONSORT guidelines and a full analysis plan developed. Descriptive statistics will be used to assess balance in the randomised arms at baseline and will be presented as means and standard deviations for normally distributed variables, medians and inter-quartile ranges for any skewed variables, or numbers and percentages.

The first part of the primary comparison will be the prevalence of antibiotic use at Day 8 post consultation (where Day 1 is the day of randomisation) between those children receiving active eardrops and those receiving no drops (usual care) and will be analysed on an intention to treat basis. The time between consultation and antibiotic consumption will also be explored. Logistic regression will be utilised and the findings adjusted for marked imbalance at baseline (e.g. that differ by more than 0.5 standard deviations for age or univariable significant differences in proportions such as those with bilateral AOM). Post randomisation health care related variables such as other analgesics taken by the child (we will record the timing of the last dose of oral analgesics given to the child that day, prior to the daily parent-rated child ear pain score) will not be adjusted for in the main model but will be mediated for in a secondary analysis. For any continuous outcomes that are clearly non-normally distributed, appropriate transformations will be documented and justified in the model. To assess the potential effects of missing data, multiple imputation methods will be utilised in a sensitivity analysis.

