Bootstrapping will be used to calculate confidence intervals around the point estimate of the incremental costeffectiveness ratio and cost-effectiveness acceptability curves. We will investigate the effect of any differences in baseline characteristics and if necessary will use regression techniques to adjust for these. To assess the potential effects of missing data, multiple imputation methods will be utilised in a sensitivity analysis. In the secondary economic analysis we will conduct a cost consequence study tabulating 3 month societal treatment costs (including data from the 3 month questionnaire and GP note review) alongside other important outcomes including 24-36 hour ear pain relief, overall symptom burden, acute illness duration (the end of which will be defined as the last day post randomisation on which parent-reported child ear pain scores zero for two consecutive days without other analgesic medication), CHU-9D utilities (in school aged children, and through multiple imputation to children outside this age range) and OMQ-14 quality of life scores.

Our study will provide decision-makers with an estimate of any incremental costs of the active intervention and any benefits in terms of reduced antibiotic prescriptions, reduced symptoms and improved quality of life. If the active intervention does reduce antibiotic use without a detrimental impact on symptoms, we will discuss the implications for parents and the NHS of making the drops available over the counter (this will be explored through the qualitative interviews). We envisage this to be part of drawing policy implications from our findings, rather than a formal extrapolation model.

A full Health Economics Analysis Plan will be developed and reviewed by the Trial Steering Committee.

Qualitative analysis

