APPENDIX 7: Study outcome definition and measurement

Research question	Question and outcome type	Outcome measure	Presented as	Method of outcome data collection
2.6 Do active drops reduce overall symptom burden (including episodes of crying/ distress, disturbed sleep, interference with normal activity, appetite and fever) in the first 7 days after randomisation compared to placebo drops and no drops (usual care)?	Secondary	Numeric: Total number of symptoms and average severity of symptoms over the first 7 days after randomisation	Mean/Median/Log mean severity of other symptoms in the first 7 days after randomisation (depending on the distribution).	Daily Symptom and Recovery Questionnaire (Days 1-8) with telephone support calls during week 1
2.7 Do active drops alter overall illness duration (defined as the last day post randomisation on which parent-reported child ear pain scores zero for two consecutive days without other analgesic medication) compared to placebo drops and no drops (usual care)?	Secondary	Numeric: number of days post randomisation on which the parent reports a score >0 for the child's ear pain or gives the child analgesics for ear pain	Number of days until child's ear pain resolves for two consective days pain free without medication (this will give us a start date but not necessarily an end date for antibiotic consumption).	Daily Symptom and Recovery Questionnaire (Days 1-8) with telephone support calls during week 1
2.8 What are the net incremental costs to the NHS (e.g. fewer antibiotic prescriptions) and society (e.g. parental productivity) of using active ear drops compared to no drops (usual care) in the short (7 days after randomisation) and medium term (3 months)?	Secondary	To be defined in the Economic Analysis Plan	To be defined in the Economic Analysis Plan	Symptom and Recovery Questionnaire (Day 8) with telephone support call, and review of primary care medical notes at 3 months
2.9 To conduct an economic analysis to explore whether the net incremental costs of active ear drops are justified by improved pain relief, symptom burden, antibiotic use or quality of life.	Secondary	To be defined in the Economic Analysis Plan	To be defined in the Economic Analysis Plan	Symptom and Recovery Questionnaire (Day 8) with telephone support call, review of primary care medical notes at 3 months, and QoL postal questionnaire at 3 months

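### Delay to antibiotics is summarised only in children who started them, and illness duration has three conflicting definitions; both are exploratory secondary outcomes

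*Protocol*

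**What the plan says.** **Delay to antibiotics.** Appendix 7, row 2.5, asks: "Do active drops alter the number of days before starting antibiotics in the first seven days post randomisation, compared with placebo drops and no drops". Its outcome-measure column gives days from randomisation to first consuming antibiotics, with no restriction. Its presentation column then restricts the result: "For children who have started taking antibiotics, the average number of days after recruitment for which antibiotics were not given (delayed". Section 12.5 adds only this: "The time between consultation and antibiotic consumption will also be explored". The outcome lists (synopsis outcome 2.5 and Section 11, item 3) name the time before antibiotics and give no rule for children who never start.

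**Illness duration.** Three quantities appear.
- Question 5.4.8, repeated in the synopsis (question 2.8) and in Appendix 7, row 2.7: "defined as the last day post randomisation on which parent-reported child ear pain scores zero for two consecutive days without other analgesic medication". The health economic part of Section 12.5 uses the same idea: "the end of which will be defined as the last day post randomisation on which parent-reported child ear pain scores zero for two consecutive days".
- Appendix 7, row 2.7, outcome measure: "number of days post randomisation on which the parent reports a score >0", or on which analgesics are given for ear pain. This is a count of days.
- Appendix 7, row 2.7, presentation: days until the pain has resolved for two consecutive days without medication. The glossary (Appendix 2) likewise defines resolution as a point in time.

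The length of the diary is also stated in two ways. Section 9.17 has Days 1 to 8 for everyone. Section 10.2 has recording continue until two days of resolution.

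**The concern.** Question 2.5 is a randomised comparison, but the children who start antibiotics are not a randomised group. Membership is decided after randomisation by the primary outcome. If drops work, the active-arm starters are a smaller and differently selected set, and the children whose antibiotic was averted leave this summary altogether. Drops that mainly prevent late starts would then appear to make parents start sooner.

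That pattern is plausible on the protocol's own rationale. Section 6.2 describes delayed prescribing as, at best, giving antibiotics only if the child is not improving after three days, with drops helping parents through that period.

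For duration, a row with three definitions leaves the choice open until after the data are seen. Read literally, the last-day wording does not measure recovery in a child who gets better and keeps filling in the diary. Duration is also tabulated in the cost-consequence study.

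**Working it through.** **1. The plan's own rates.** Section 12.1 says the number per arm "ranges from 92 to 119 to demonstrate a 20% fall in antibiotic consumption from 80-90% in the control group to 60-70" per cent, with the error rates given as: "Assuming a Type II error rate of 0.1 (90% power) and Type I error rate of 0.05 (alpha". The two-sided pooled formula with continuity correction gives 119 for 80% v 60% and 92 for 90% v 70%; 119/0.8 = 148.75, so 149. The stated figures reproduce, and 80% v 60% is used below. No stated sample size depends on this point.

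**2. Assumed start days.** The protocol gives none. Assume that, among no-drops starters, delays of 0 to 7 days have proportions 0.05, 0.25, 0.20, 0.20, 0.12, 0.08, 0.06 and 0.04. The mean is 0.25 + 0.40 + 0.60 + 0.48 + 0.40 + 0.36 + 0.28 = 2.77 days.

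**3. Two measures.** With p_d the proportion of all children starting at delay d, and P their sum:
- starters only: sum(d × p_d) / P
- all children, antibiotic-free days restricted to 7: sum(d × p_d) + 7 × (1 - P)

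No drops (P = 0.80): starters 2.77; all children 0.80 × 2.77 + 7 × 0.20 = 3.62.

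Active (P = 0.60), by which starts are averted:
- Latest: sum = 0.20 + 0.32 + 0.48 + 0.16 = 1.16; starters 1.16/0.60 = 1.93; all 1.16 + 2.80 = 3.96.
- Evenly: sum = 0.60 × 2.77 = 1.66; starters 2.77; all 4.46.
- Earliest: sum = 0.04 + 0.32 + 0.48 + 0.384 + 0.32 + 0.288 + 0.224 = 2.056; starters 3.43; all 4.86.

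| Starts averted | Starters only, active minus no drops | All children |
|---|---|---|
| Latest | -0.84 d | +0.34 d |
| Evenly | 0.00 d | +0.85 d |
| Earliest | +0.66 d | +1.24 d |

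At 90% v 70% the differences are -0.76, 0.00 and +0.57 d (starters) and +0.31, +0.85 and +1.25 d (all children).

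**4. Variations at 80% v 60%.**
- Latest starts averted, and every remaining starter also delayed by 0.5 d: starters 1.93 + 0.50 - 2.77 = -0.34 d; all children 0.34 + 0.5 × 0.60 = +0.64 d. Drops both reduce and delay use, yet the starters-only sign is wrong.
- Averted starts only moderately weighted to late days (in proportion to d + 1): starters-only difference -0.28 d. With 134 children analysed per arm, about 86% of simulated trials had the wrong sign, and about 18% were significant at 5% in the wrong direction.
- Constant hazard, rate = -ln(1 - P)/7, starters' mean = 1/rate - 7(1 - P)/P: 2.60 v 2.97 d (+0.37). All children, P/rate: 3.48 v 4.58 d (+1.10). Here the sign is right.

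**5. Duration.** Assume a lognormal time to resolution with median 3 days and 90% resolved by 8 days (both from the protocol), so sigma = ln(8/3)/1.2816 = 0.765. Assume durations 25% shorter on active drops.
- First pain-free day, mean: 5.52 v 4.52, a difference of 1.00 d.
- Literal last day with a full Day 1-8 diary: a child scores exactly 8 if resolved within 6 days. The shares are Phi(ln(6/3)/0.765) = 0.82 and Phi(ln(6/2.25)/0.765) = 0.90. The means are 8.78 v 8.37, a difference of 0.41 d.
- If recording stops at two resolved days, the last and first such pairs coincide and nothing is lost.

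For a child with no relapse, the day count and the days to resolution agree: pain on Days 1 and 2 and none from Day 3 gives 2 on both. They part when pain returns. With pain on Days 1, 2, 5 and 6 only, and no analgesics, the count is 4, while first resolution (Day 3) comes 2 days after randomisation.

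**The case against.** The restriction to starters sits in one column of one appendix table. The outcome-measure column beside it and the outcome lists are unrestricted, and Section 12.5 promises appropriate regression methods and a full analysis plan. Choice of model and censoring can properly be left to that plan. This stands as to method. It does not rescue the summary, because the protocol itself fixes the population for the between-arm question and nothing elsewhere overrides it. It is also fair that averted children are still counted in the primary outcome; they are lost only from this summary.

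A reader might infer that the starters-only result will be reversed. The documents do not support that. The sign depends on which starts are averted, which nobody knows in advance; it is right if early starts are averted or under a constant hazard.

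A reader might also infer that the last-day wording hides any effect on duration. That assumes every parent completes all eight days. Section 10.2, the symptom-severity outcome in Section 11 and inclusion criterion 11 in Section 6.2 all have recording or follow-up ending at resolution, and then there is no error. Even with a full diary the effect shrinks rather than vanishes. The glossary and the purpose of the calls after Day 8 show that time to resolution is the likely intent.

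Finally, the day count cannot be fully observed after Day 8, when calls are twice weekly. That concerns the roughly 10% still symptomatic, and it argues for the time-to-resolution definition already in the row.

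**Conclusion.** The delay summary is wrongly specified for a randomised comparison. At the planned 80% v 60% it can run from -0.84 to +0.66 days, while the all-children measure stays positive, from +0.34 to +1.24 days. These sizes rest on assumed start-day patterns. The flaw itself, conditioning on the primary outcome, needs no assumption.

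For illness duration the secure finding is inconsistency: three definitions, together with two statements of how long the diary runs. The loss from 1.00 to 0.41 days applies only to the literal reading with a full diary, and it rests on the lognormal shape and the assumed 25% shortening.

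Both are secondary outcomes that Section 12.5 treats as exploratory, and neither enters the recommendation rules in Section 4.3. The primary conclusion, the key secondary outcome and the target of 501 are untouched. The point should be corrected before analysis, but it is not a reason to question the trial's main result.

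**What to change.** **Delay.** In Appendix 7, row 2.5, and Section 12.5, define the outcome as time from randomisation to first antibiotic dose in all randomised children, with children who do not start censored at Day 8. Either a time-to-event analysis or restricted mean antibiotic-free days to Day 8 would serve; the analysis plan can choose. Keep mean delay among starters as a descriptive figure with no between-arm test.

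**Duration.** Use one definition throughout: days from randomisation to the first day of the first two consecutive days with pain score zero and no analgesic, censored at last contact (calls run to a maximum of four weeks under Section 9.20). Remove the last-day wording from synopsis question 2.8, question 5.4.8, Section 12.5 and Appendix 7, row 2.7, and remove the day count from that row. Reconcile Sections 9.17 and 10.2 on when the diary ends, and add the calls after Day 8 to the row's data-collection column.

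**Cost.** Wording only. The daily diary and the later calls already collect what is needed.
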